- *Each study site to describe the source population and definition of the study cohort Each study site to specify the target groups for which influenza vaccination is recommended, which vaccines are used in the database catchment area, and how the choice of vaccine brand happens*

Study period

The study follow-up will start before the seasonal influenza vaccine is available and before the influenza virus circulation begins in the country/region, to ensure that all vaccinations and all outcomes in the defined cohort are captured. If only aggregated data will be collected that does not allow the shortening of the study subjects' follow-up as part of the statistical analysis, the follow-up may be restricted to the time the vaccine first becomes available or the virus circulation starts, whichever occurs first. The study period will finish at the end of the influenza season.

- *Each study site to specify the study period: the definition of the beginning and end of the study period*
- *Each study site to specify the early, middle and end of the influenza epidemic at the study site according to the information provided by the local influenza surveillance system.*

For the pooled analysis, a harmonised minimum period will be defined (e.g. from week 40 till week 20), but if needed, it will be extended to fully cover the vaccination campaign and the epidemic in each study site. Definition of shorter time periods (e.g. early, middle and end season) will be developed to take into account differences in influenza activity over time and probable development of immunity in unvaccinated population through encounters with the circulating viruses

For addressing the secondary objective of estimating influenza vaccine effectiveness over several seasons, multiple study periods will be combined. If possible, the information from the local surveillance systems of major circulating strains in the study regions will be considered in the analysis. The details of the analysis will be described in the generic study site level SAP.

Study population and follow-up

Cohort of interest

The study cohort comprises the characterised by place of residence, or catchment population of a health care service providing the relevant information for the analyses. The databases may also be characterised by or restricted to e.g. age, or medical, physiological or occupational conditions (e.g. pregnancy, health care workers, other risk/target groups).

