The cohort should be restricted to and include all individuals eligible for the defined exposure (e.g. children at least 6 months of age in the beginning of the follow-up), for which data of the exposure (i.e. influenza vaccination status including brand information), the defined outcome(s), and at least the defined minimum, preferably the most important set of potential confounders and effect modifiers can be retrieved reliably enough (See sections Exposure, Outcome, and Confounders and effect modifiers and Potential biases).

Instead, restricting the cohort with any exclusion criteria based on potential individual confounders or effect modifiers is not advisable, since this includes a risk of selecting the population also by other, unknown underlying factors. Instead, individual analyses may be restricted to defined subpopulations, or stratified or sensitivity analyses may be conducted.

For an analysis adjusted by chronic conditions, the cohort should be defined according to the availability of either historic diagnostic data or e.g. data on recent medications used to treat chronic conditions or permanent reimbursement status for such medications. The harmonisation of the data used for adjusted analyses will be performed between study sites after evaluating the characteristics and structure of the databases available and their potential validation information.

The follow-up

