The exposure of interest is vaccination with any seasonal influenza vaccine in the season under investigation (index season). For vaccination status ascertainment, it is crucial to know about the date of vaccine administration and the type/brand of the vaccine. .

The sources of information for the vaccination status may include:

- vaccination registry
- health care visit/hospitalisation register with relevant information of the vaccinations
- relevant insurance company register or prescription register showing evidence of pharmacy delivery or reimbursement of influenza vaccine

- *Each study site to describe the precise way of vaccination status ascertainment.*

Definition of vaccination status

An individual aged ≥ 9 years, or a child aged <9 who has been fully vaccinated before the current season (at least two injectable doses or one LAIV dose) will be considered as

- **vaccinated** with the influenza vaccine of interest (defined exposure) if >14 days have elapsed since the first record of influenza vaccination during the season (see section *Vaccination status ascertainment*)
- **partially vaccinated** during the first 14 days after the first record of vaccination (defined exposure) during the season
- **unvaccinated** until the first vaccination record during the season

A child aged <9 years who has not been fully vaccinated (see above) before the current season will be considered as

- **vaccinated** with the influenza vaccine of interest if >14 days have elapsed since the second record of injectable vaccination or the first record of LAIV vaccination during the current season (see section *Vaccination status ascertainment*)
- **partially vaccinated**
 - during the first 14 days after the second record of injectable vaccination or the first record of LAIV vaccination during the current season
 - after the first record of injectable vaccination until >14 days have elapsed since the second record of vaccination during the current season
- **unvaccinated** until the first vaccination record during the season

If vaccination cannot be assessed as a time-dependent event, and for the description of demographics and baseline characteristics, the vaccination status (yes/no) will be assessed at the end of the individual follow-up.

If the individual has a record of vaccination with a type or brand other than the one of interest (defined exposure) during the study period, she/he will be right-censored at this time point (see section Individual follow-up).

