- *Each study site to specify the data checking and cleaning process*

Statistical analysis

This section describes the main principles for the study site level analysis. The statistical analyses are attempted to be harmonised between the study sites, to optimise the numbers of variables to be used in the adjustment and the heterogeneity/homogeneity between the study sites. After analysing the characteristics and structure of the databases used in participating study sites, a generic site level Statistical Analysis Plan (SAP) will be provided, including guidelines for harmonisation, with details/alternatives for defining the variables. The generic site level SAP will be updated annually, and attached as an Annex 2 to the generic protocols. Details on the site-specific analyses will be provided in the site-specific Statistical Analysis Plans (SAPs), attached as Annexes of the site-specific protocols. Information on the two-stage pooling of data from several study sites is provided in the DRIVE D4.4: “*Generic statistical analysis plan; combining information on influenza vaccine effectiveness across study sites.*” Based on the D4.4, season-specific SAPs for pooling data across study sites will be written. The season-specific SAP is expected to be modified each season to reflect the specificities of the season’s influenza epidemic as well as changes in participating study sites and data availability.

Individual follow-up

The follow-up of an individual belonging to the defined study cohort starts at a fixed time point at the start of the study period, and the follow-up continues until the first occurrence of the defined outcome, until another event leading to right-censoring as defined below, or until the end of the study period, whichever comes first.

Study subjects are right-censored, i.e. their individual follow-up ends, after the first occurrence of the outcome defined for the analysis in question. Other reasons for right-censoring have to be defined according to data availability and harmonised between the study sites: death, moving out of from the cohort catchment area, administration of an influenza vaccine of a type or brand other than the exposure defined for the analysis, having and influenza infection caused by an influenza virus type/subtype/lineage other than the one defined as the outcome for the analysis.

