Annex 1: The dataset

Annex 1 defines the data elements to be used for estimating brand-specific VE in a population based cohort study using secondary data from pre-existing databases. The minimum dataset is marked with an asterisk(*), but preferably the most important covariates to adjust for will be included. According to these data elements, the analysis database will be developed to include the defined outcome events by person months vaccinated, (partially vaccinated) and unvaccinated, considering the events leading to right-censoring, and the covariates needed for adjustment or stratification.

The database may alternatively be structured for aggregated data, initially based on these data elements.

Instructions for harmonisation of the variables and the structure of analysis database will be provided in the generic study site level Statistical Analysis Plan (SAP), Annex 2. Season-specific updates in Annex 2 will be implemented to Annex 1, if needed.

DRIVE – The dataset for estimating VE in a population based cohort study using secondary data from pre-existing databases. The minimum data set is marked with an asterisk(*)�.

	Variable	Description	Format	Values and coding	Example
General	idcountry*	Country code defined in ISO 3166-1 alpha-2	2 letters text		Finland
	id*	Patient or aggregate identification number	Unique integer		12345678
	cohort*	Cohort name	Text		THL
	region*	Region name	Text		Pirkanmaa
	dataset*	Data set name	text		Elderly
	sex*	Sex	Numeric (Binary)	0=Female 1=Male	0
	dob* (alternatively age)	Date of birth or age at the start of the follow-up (children: months; adults:years)	dd/mm/yyyy	Date between the date of birth of the oldest and youngest study subject	01/01/1960

The follow-up	startdate*	Date of the start of the study period	dd/mm/yyyy	Date within the study period	30/12/2017
	enddate*	Date of the end of the study period ^a	dd/mm/yyyy	Date within the study period	30/12/2017
	middledate	Date separating the early and the middle epidemic season	dd/mm/yyyy	Date within the study period	30/12/2017
	latedate	Date separating the middle and the end epidemic season	dd/mm/yyyy	Date within the study period	30/12/2017
	death*	Died during the follow-up	Numeric (Binary)	0=No 1=Yes	1
	deathdate*	Date of death ^a	dd/mm/yyyy	Date within the study period	30/12/2017
	moved(*)	Moved out of the cohort catchment area during the follow-up	Numeric (Binary)	0=No 1=Yes	1

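### For under-9s given injectable vaccine, Annex 1's starred minimum dataset cannot apply the protocol's two-dose exposure rule after day 14 from dose 1

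*Combined protocol and SAP*

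**What the plan says.** Definition of vaccination status (under Exposure) sets two rules for children under 9. The first applies to a child who was "fully vaccinated before the current season (at least two injectable doses or one LAIV dose" mentioned there: such a child is treated like anyone aged 9 or over and is vaccinated once more than 14 days have passed since the first record of the season. Any other child is vaccinated only "if >14 days have elapsed since the second record of injectable vaccination or the first record of LAIV vaccination during the current season". With injectable vaccine, that child is partially vaccinated from dose 1 until more than 14 days after dose 2.

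The section's one fallback begins "If vaccination cannot be assessed as a time-dependent event" and then uses yes/no status at the end of individual follow-up.

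Annex 1 states: "The minimum dataset is marked with an asterisk(*), but preferably the most important covariates to adjust for will be included". In the exposure and history rows:

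- **Starred:** `inflvacdate`, `brandXdate1`, `vactypeXdate1`, which are all first dates.
- **Not starred:** `inflvacdate2`, `brandXdate2`, `vactypeXdate2`, `seasvacn1`, `seasvacn2`.

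Footnote d, attached to the first dates, says that one of them serves as the exposure date of the analysis. Footnote e reserves the second dates for under-9s without earlier full vaccination.

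Cohort of interest limits the cohort to people whose exposure data, described as "influenza vaccination status including brand information", can be retrieved reliably enough, and it refers the reader to the Exposure section.

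**The concern.** The exposure rule and the minimum dataset do not fit together. The rule for injectable vaccine in under-9s depends on two items, and the minimum dataset requires neither. Footnote e shows that the need for second dates was recognised, but the fields were left optional, and footnote d directs the reader to a first date.

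Children from 6 months of age are in scope, brand- and type-specific VE is the primary objective, and VE by age group is a secondary one. A site that holds only the starred fields and starts exposed time 15 days after dose 1 would count partially vaccinated time as vaccinated. If other sites apply the two-dose rule, the pooled children's estimate for injectable vaccine combines two exposure definitions.

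**Working it through.** **Can status be assigned from starred fields?** Take age, first-dose date and first-dose type as known. Leave earlier full vaccination (yes/no) and dose 2 (none, day 28 or day 42 after dose 1) unknown. Then apply the rule (P = partially vaccinated, V = vaccinated):

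| Days since dose 1 | Injectable | LAIV |
|---|---|---|
| before dose 1 | unvaccinated | unvaccinated |
| 0, 7, 14 | P | P |
| 15, 28, 42, 43, 100 | P or V: undetermined | V |

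LAIV is settled throughout. Injectable vaccine is unsettled on every tested day from 15 on.

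**Is one missing item enough?** No.

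- Day 15: history alone settles status (V if fully vaccinated earlier, otherwise P). The second-dose date alone does not.
- Days 43 and 100, history 'no': still P or V without the second-dose date.
- Days 43 and 100, no second dose: still P or V without history.
- Any day after 14, history 'yes': V from dose 1 alone, with no second date needed.

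**Does the listed history cover the rule?** Only in part. `seasvacn1` and `seasvacn2` reach back two seasons, while the rule counts doses from any earlier season.

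**Size, as illustration only.** None of the inputs below is a figure the plan gives for this purpose, except that the season length follows its example of weeks 40 to 20. The plan states that "The study follow-up will start before the seasonal influenza vaccine is available and before the influenza virus circulation begins in the country/region", so the start of circulation relative to vaccination is a free input.

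- Season: 33 weeks × 7 = 231 days (days 0–230), constant incidence once circulation starts on day c.
- Dose 1 on day 30; dose 2 on day 30 + 28 = 58.
- Two-dose VE 50%; one-dose VE V1 from 0 to 30%.
- h = share of vaccinated under-9s already fully vaccinated earlier; q = share of the others who stop at one dose.

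Counting from dose 1, vaccinated time starts on day 30 + 15 = 45. Under the two-dose rule it starts on day 58 + 15 = 73. With s = max(45, c), the misclassified share among two-dose children is m = max(0, 73 − s)/(231 − s). Overall p = (1 − h)[q + (1 − q)m], and measured VE = (1 − p) × 50% + p × V1.

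| c | h | q | p | Measured VE |
|---|---|---|---|---|
| ≤ 45 | 0 | 0 | 28/186 = 0.151 | 42.5–47.0% |
| 60 | 0 | 0 | 13/171 = 0.076 | 46.2–48.5% |
| ≥ 73 | 0 | 0 | 0 | 50% (no bias) |
| 73 | 0 | 0.3 | 0.30 | 35.0–44.0% |
| 73 | 0.5 | 0.3 | 0.5 × 0.3 = 0.15 | 42.5–47.0% |

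The result is driven by q, h and the start of circulation, none of which the documents give.

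**The case against.** The best defence is that Cohort of interest already deals with this. It demands reliably retrievable vaccination status and points to the section that holds the two-dose rule, so a site unable to apply that rule has not retrieved the status and should leave those children out. Each site must also describe how it ascertains status.

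Annex 1 is a single list for all cohorts (its example dataset is elderly), so leaving child-only fields unstarred is understandable. Changes to the protocol says the minimum dataset is still to be developed, and Annex 2 is to give harmonisation instructions and feed updates back into Annex 1. Bias arises only if a site departs from the written rule. The documents describe no site that holds first dates without second dates, and both would normally come from the same register. Missing data allows subjects without historical background data to be left out of adjusted analyses, and Sensitivity analyses already lists one-dose and two-dose VE in children.

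Much of this stands, and it limits the weight of the point. It does not remove the inconsistency. No text says that first dates are insufficient for under-9s, while the asterisks and footnote d suggest that they suffice. The stated fallback covers missing timing, not a missing second dose or missing history. The promised updates do not name this gap.

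**Conclusion.** The inconsistency is real and follows from the text alone: a site supplying exactly the stated minimum dataset cannot apply the stated exposure rule to under-9s given injectable vaccine once 14 days have passed since dose 1. It should be corrected. Ages 9 and over, LAIV recipients, cohorts without under-9s, and sites that supply second-dose dates and adequate history are unaffected.

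A reader might infer more than the documents support:

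- **That children's VE will be biased downwards by a known amount.** The figures above rest wholly on assumed inputs. The direction assumes that one dose protects less than two, and the bias can be zero.
- **That the protocol permits counting from dose 1.** It does not. The rule calls that time partially vaccinated, and Cohort of interest points towards leaving out children whose status is unreliable. The fault is that Annex 1 invites the error.
- **That Annex 1 lacks the fields.** They are listed, but outside the minimum set.
- **That '(*)' is already a conditional mark.** It appears on the row "Moved out of the cohort catchment area during the follow-up", but the legend does not define it that way.
- **That every under-9 without a second date is unusable.** Children known to have been fully vaccinated earlier can be classified from dose 1 alone.

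**What to change.** **Annex 1.** Mark `inflvacdate2`, `brandXdate2` and `vactypeXdate2` as required for cohorts that include under-9s given injectable vaccine, and define that conditional mark in the legend. Add one required field for under-9s recording full vaccination in earlier seasons:

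- 'yes' if `seasvacn1` or `seasvacn2` is code 1, if both are code 2 (one injectable dose in each season), or if older records show at least two injectable doses or one LAIV dose;
- 'no' only if records cover every earlier season in which the child was eligible;
- 'no information' otherwise.

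**Fallback, stated by case:**

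- (a) History 'yes': classify from dose 1; no second date is needed.
- (b) History 'no', second-dose dates available: apply the two-dose rule.
- (c) History 'no', second-dose dates not available: count as partially vaccinated from dose 1, or right-censor at the first injectable dose.
- (d) History 'no information': right-censor at the first injectable dose and keep the earlier unvaccinated time.

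A site that can supply neither item right-censors as in (d), or excludes all under-9s under Cohort of interest. It must never drop only those later vaccinated, because that selects on future exposure. Censoring at a dose is not new to this plan: Individual follow-up already lists "administration of an influenza vaccine of a type or brand other than the exposure defined for the analysis" as a reason. Any analysis of at least one dose should be a labelled sensitivity analysis, in line with the existing list.

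**Cost.** Three marks, one legend line, one derived field and a short paragraph. Intervals for injectable VE in young children widen at sites without these data. Under censoring, LAIV estimates are kept; a site that excludes all under-9s loses them for that age group.

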Thus, each study subject may contribute to the follow-up time (person time) as unvaccinated, as partly vaccinated and as vaccinated, according to the definitions in section Exposure, Definition of vaccination status.

Disease episode

Repeated influenza infections during a season are extremely rare, and the first influenza infection affects the probability of the second one. Thus, for specific outcomes, only the first record is considered. However, in addition to the date of the laboratory test for positive influenza finding, the outcome date may be defined as a few days before the test as a proxy for the symptom onset, e.g. for sensitivity analysis.

Instead, there may be repeated visits because of reasons compatible with the non-specific outcomes, e.g. primary care visits before hospitalisation. Outcome-specific definitions for a disease episode will be needed to define the vaccination status at the time of the onset of the disease episode and to indicate which outcome measures are considered to belong to the same disease episode. Outcome-specific definitions for a disease episode are included in the generic site-specific statistical analysis plan (SAP) (Annex 2), to allow harmonization between the individual site-specific analysis plans.

Demographics and baseline characteristics

The baseline characteristics of the study cohort will be described and tabulated by exposure status at the end of the individual follow-up. The association between the baseline characteristics and the exposure status will be investigated using the Fisher's exact test (in case of nominal variables for the baseline characteristics), Mann-Whitney test (in case of ordinal or non-normal continuous variables) or Student's t-test (in case of normal variables). The description of the baseline characteristics will be stratified by the vaccination status at the end of the follow-up and by most important outcome(s) (e.g. laboratory confirmed influenza cases versus others). The proportion of positive influenza tests of all obtained tests will be described, if available.

Measure of effect

The crude (or unadjusted) brand-specific IVE will be estimated as

$$VE = (1 - RR) \times 100\%,$$

where RR denotes the relative risk (ratio of probabilities) or rate ratio (ratio of incidence or hazard rates) of the outcome n for vaccinated individuals versus unvaccinated individuals. The 95% confidence intervals will be calculated as well.

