The analysis must be conducted for each exposure and outcome of interest separately. Confounder-adjusted brand-specific, type specific or overall IVE estimates will be obtained from multivariable regression models, regressing the health outcomes of interest on exposure status, age, sex and the confounders of interest. In case of effect modifiers, an interaction term between exposure and the effect modifier will be included in the regression model or stratified regression analyses will be performed.

Depending on the type of data available, the analytical method(s) will be described in the generic study site level SAP and in a study-specific SAP before the start of the study period. For the outcome of interest, irrespective of its type, multivariable logistic regression will be used, if only the number of events as vaccinated and unvaccinated by number of subjects vaccinated and unvaccinated at the end of the follow-up is known. If the number of events by person time and vaccination status can be assessed, Poisson regression will be used. In case of time-to-event data, Cox regression (proportional hazards) will be used.

Missing data

The cohort should be defined so that the missing data is minimised: the cohort should cover all subjects targeted, especially for the vaccination, and only those subjects. Especially the outcome should be caught non-differentially, i.e. similarly for vaccinated and unvaccinated (see section Study population and follow-up; Cohort of interest). Missing data for events occurring during the follow-up is not available, since 'no record' means by definition 'no event' (unless also the negative

outcome information, e.g. negative influenza tests are available, when a nested case control analysis could be performed).

Missing data may be present, if historical data for background factors at start of the follow-up is not available, e.g. if the subject has moved into the attachment area of the database recently, or it is incomplete, e.g. only part of the databases used in defining the different background factors are available. This subcohort may be excluded from the adjusted analyses.

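### In the fallback for sites without time-dependent vaccination, status fixed at the end of follow-up builds in immortal time, and logistic regression reports an odds ratio where VE is defined by a risk or rate ratio

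*Combined protocol and SAP*

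**What the plan says.** The default is sound in outline. Definition of vaccination status sets out unvaccinated, partially vaccinated and vaccinated periods. Individual follow-up lets one person contribute time to each. Measure of effect assigns Poisson regression to events by person-time and Cox regression to time-to-event data.

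The point concerns the fallback. Definition of vaccination status opens it with a condition, "If vaccination cannot be assessed as a time-dependent event, and for the description of demographics and baseline characteristics", and then states that "the vaccination status (yes/no) will be assessed at the end of the individual follow-up". Measure of effect adds that "multivariable logistic regression will be used, if only the number of events as vaccinated and unvaccinated by number of subjects vaccinated and unvaccinated". Those counts are by final status, and the rule applies whatever the type of outcome.

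Three other provisions matter:

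- Individual follow-up: a person's time runs "until the first occurrence of the defined outcome, until another event leading to right-censoring as defined below", or to the end of the study period.
- Study period: "The study follow-up will start before the seasonal influenza vaccine is available and before the influenza virus circulation begins". With aggregated data it may instead start at vaccine availability or at virus circulation, whichever is earlier.
- Measure of effect: VE is 1 − RR, "where RR denotes the relative risk (ratio of probabilities) or rate ratio (ratio of incidence or hazard rates". The odds ratio is not among these, and no conversion is given.

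Addressing confounding & bias does not mention immortal time, and none of the listed sensitivity analyses targets it.

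**The concern.** Under the fallback, the outcome itself decides exposure for some people. Someone who intended to be vaccinated in week 50 but is infected in week 49 leaves follow-up unvaccinated, and so adds a case to the comparator. Someone vaccinated in week 50 must have been event-free until then, and that event-free time is credited to the vaccinated group. Both shifts raise VE even if the vaccine does nothing. A larger cohort does not reduce the error; it only narrows the interval around it.

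The second issue is the scale. When RR is below 1, the odds ratio lies further from 1 than the risk ratio, so 1 − OR exceeds 1 − RR.

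At stake are the brand-specific, type-specific and overall VE estimates from any site that supplies only counts by final status.

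**Working it through.** **Inputs from the documents.** Attack rate (AR) in the unvaccinated 5% and 15%; coverage 20%, 50% and 70%; true VE 50%; N = 5000 (Sample size considerations and Annex 3). A 14-day partial-vaccination window (Definition of vaccination status). An example study period of week 40 to week 20, about 33 weeks or 231 days (Study period).

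**Assumed, because the documents give no timing.** Vaccination weeks, start of circulation and shape of the epidemic.

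**1. The plan's own precision figure.** Annex 3, equation (3), N = 5000, coverage 50%: A₁ = 62.5, A₀ = 125, N₁ = N₀ = 2500. The standard error is √(0.016 − 0.0004 + 0.008 − 0.0004) = 0.1523. The lower limit is 1 − 0.5·exp(1.96 × 0.1523) = 32.6%. At coverages of 20%, 21% and 70% it is 24.7%, 25.3% and 32.3%. The stated limit above 25% for coverages above 20% reproduces.

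**2. Immortal time, true VE 0.** Assume vaccination uniform from week 42 to week 52, circulation from week 47, and constant hazard for 14 weeks. Cumulative hazard is −ln(1 − 0.05) = 0.0513. Half of the vaccinees are vaccinated after week 47, on average 2.5 weeks into circulation. The share of planned vaccinees infected first is about 0.5 × (2.5/14) × 0.0513 = 0.00458. Per 1000 people at 50% coverage this is 2.29 people:

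- Vaccinated: (25 − 2.29)/(500 − 2.29) = 4.563%.
- Unvaccinated: (25 + 2.29)/(500 + 2.29) = 5.433%.
- RR = 0.840, so false VE is about 16%.

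Full integration of the hazard gives 10.6%, 15.9% and 23.9% at coverages of 20%, 50% and 70%. If vaccination continues to the end of week 52, the values are about 14%, 20% and 30%. If it ends before week 47, the false VE is 0.

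**3. Sensitivity to timing.** Day-by-day model over 231 days, coverage 50%, AR 5%, true VE 0, campaign uniform from the start of follow-up, epidemic peak with SD 3 weeks. False VE on the risk-ratio scale:

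| Campaign | Peak week 18 | Peak week 12 | Peak week 8 | Constant risk |
|---|---|---|---|---|
| 8 weeks | 0.0% | 2.7% | 23.5% | 20.7% |
| 12 weeks | 0.4% | 16.7% | 48.4% | 29.7% |
| 16 weeks | 5.0% | 38.8% | 64.2% | 37.8% |

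The constant-risk column stands for a non-specific outcome that occurs all season.

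**4. True VE 50%, timings of step 2 (campaign ending at week 52).** VE is set as a hazard reduction, so without immortal time the risk-ratio VE would be 1 − (1 − 0.95^0.5)/0.05 = 49.4%. The fallback gives 54.8%, 57.5% and 61.5% at coverages of 20%, 50% and 70%. If the first 14 days after vaccination are unprotected but counted as vaccinated, it gives 50.6%, 53.5% and 57.9%.

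**5. Odds ratio read as RR.** With p₁ = p₀(1 − VE), OR = [p₁/(1 − p₁)]/[p₀/(1 − p₀)]. At true VE 50%:

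- AR 5%: (0.025/0.975)/(0.05/0.95) = 0.487, apparent VE 51.3% (+1.3 points).
- AR 15%: (0.075/0.925)/(0.15/0.85) = 0.459, apparent VE 54.1% (+4.1 points).

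**6. After time-splitting.** In the step 3 model with 8- or 12-week campaigns and coverage 50%, rate ratios stratified by calendar day return 0.0% for true 0% and 50.0% for true 50% at every epidemic timing. Weekly strata (8-week campaign) are within 0.3 points, and 28-day strata are within about 4 points.

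**The case against.** The best defence is scope. The rule is conditional, and its other stated use is baseline tables, which estimate no effect. The protocol says of vaccination that "it is crucial to know about the date of vaccine administration and the type/brand of the vaccine"; Annex 1 marks vaccination and influenza-test dates as minimum data and plans events by person-months and status. A site that meets this dataset should not need the fallback, and no site is named that will use it. Annex 2, which will hold the detailed methods, is still to be written. All of this stands and limits the reach of the point. It does not remove it: Study period and Annex 1 expressly admit aggregated data, and Measure of effect prescribes the analysis for final-status counts.

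A second defence is that the net bias need not be upward. The 14-day window works the other way, as step 4 shows. So could the handling of other-brand vaccinees: if they are kept as unvaccinated after censoring, a brand-specific VE of 50% falls to about 18–32% (8-week campaign, coverage 50%, brand share 40%). Annex 3 suggests that they are excluded, but the text on the fallback does not say so. These are separate errors, and an uncertain cancellation is no safeguard.

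Third, the odds-ratio part is small. At AR 5% it is 1.3 points, against a lower limit that lies 17.4 points below the assumed VE at N = 5000 and coverage 50% (50 − 32.6). That is fair; it is the minor part.

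Two stronger readings are tempting. A reader might infer that the main analysis is biased in this way; it is not, because time-split Poisson or Cox analyses do not use end-of-follow-up status. A reader might also infer that odds ratios, rate ratios and hazard ratios will be pooled as one measure. The protocol places pooling in a separate generic plan (D4.4) and in season-specific plans that are not supplied, so this cannot be established either way.

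**Conclusion.** The concern holds for the fallback only. Fixing yes/no status at the end of individual follow-up, when follow-up stops at the outcome, creates immortal time and biases VE upward whenever vaccination overlaps the risk period. With a campaign that overlaps the first weeks of circulation, false VE at true VE 0 is about 10–30% across coverages of 20–70%. It is zero if vaccination finishes first. Step 3 shows that it can be larger with a long campaign and an early epidemic. All these sizes rest on assumed timings, and counting the first 14 days as vaccinated offsets part of the bias.

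Separately, the prescribed logistic model does not estimate the RR in the protocol's definition of VE. At true VE 50% this adds 1.3 points at AR 5% and 4.1 points at AR 15%.

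**What to change.** Amend Definition of vaccination status and Measure of effect, and carry the change into Annex 2:

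- Require vaccination and outcome dates, which are already asterisked in Annex 1. From aggregate-data sites, require events and person-time by vaccination status and calendar period.
- Analyse these by Poisson regression with calendar-time strata. The strata are needed: crude Poisson without them gave VE between −37% and +14% at true VE 0 (8-week campaign, coverage 50%), and the protocol does not specify calendar-time adjustment. Weekly periods suffice on the figures in step 6.
- Where only end-of-follow-up counts exist, use log-binomial or robust Poisson regression so that the output is a risk ratio. Label the estimate as prone to immortal-time bias, and report it only in a sensitivity analysis, outside the primary pooled estimate.

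The cost is a changed count request and possibly a few sites lost from the primary pool.

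A landmark analysis (status fixed at the start of circulation, later events only) should not be the default. With the step 2 timings (campaign ending at week 52), landmark week 47 and true VE 50%, it returns 47.0%, 41.5% and 35.3% at coverages of 20%, 50% and 70%, because late vaccinees stay in the comparator. At 50% and 70% coverage the losses of 8.5 and 14.7 points exceed the upward errors of 7.5 and 11.5 points that it would remove (step 4, without the 14-day offset).
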